10.1.4. Data protection

Participants will be assigned a unique identifier by the investigator. Any participant records or datasets transferred to the sponsor will contain only the identifier. Name and any other information which would identify the participant will not be transferred.

GSK will ensure protection of the personal data of the investigator and site staff which is collected within the framework of and for the purpose of the study.

The participants' parent(s)/LAR(s) must be informed that:

- Their child's/ward's study-related data will be used by the sponsor in accordance with local data protection law.
- Their child's/ward's may be examined by Clinical Quality Assurance auditors or other authorized personnel appointed by the sponsor, by appropriate IRB/IEC members, and by inspectors from regulatory authorities.

The participants' parent(s)/LAR(s) must be notified about their rights regarding the use of their personal data in accordance with the data privacy section of the ICF.

10.1.5. Committees structure

GSK will obtain favorable opinion/approval to conduct the study from the appropriate regulatory agency, in accordance with applicable regulatory requirements, prior to a site initiating the study in that country. This includes IRBs/IECs for review and approval of the protocol and subsequent amendments, ICF and any other documentation.

10.1.6. Dissemination of clinical study data

The key design elements of this protocol and results summaries will be posted on www.ClinicalTrials.gov and/or GSK Clinical Study Register in compliance with applicable regulations/GSK policy. GSK will aim to register protocols summaries prior to study start and target results summaries submission within 12 months of primary/ study completion date. Where external regulations require earlier disclosure, GSK will follow those timelines.

Where required by regulation, summaries will also be posted on applicable national or regional clinical study registers. Where required by applicable regulatory requirements, an investigator signatory will be identified for the approval of the study report, and provided reasonable access to statistical tables, figures, and relevant reports. GSK will also provide the investigator with the full summary of the study results. The investigator is encouraged to share the summary results with the study participants, as appropriate.

GSK will provide the investigator with the randomization codes for their site only after completion of the full statistical analysis.

GSK intends to make anonymized patient-level data from this study available to external researchers for scientific analyses or to conduct further research that can help advance medical science or improve patient care. This helps ensure the data provided by study participants are used to maximum effect in the creation of knowledge and understanding.

10.1.7. Data quality assurance

The investigator should maintain a record of the location(s) of their respective essential documents, including source documents. The document storage system used during the study and for archiving (irrespective of the type of media used) should provide for document identification, version history, search, and retrieval.

Essential study documents may be added or removed where justified (in advance of study initiation) based on their importance and relevance to the study. When a copy is used to replace an original document (e.g., source documents, CRF), the copy should fulfill the requirements for certified copies.

All participant data related to the study will be recorded on printed or electronic CRF unless transmitted to the sponsor or designee electronically (e.g., laboratory data). The investigator is responsible for verifying that data entries are accurate and correct by physically or electronically signing the eCRF.

The investigator must maintain adequate and accurate source documents and study records that include all pertinent observations on each of the site's study participants that supports information entered in the eCRF.

The investigator must permit study-related monitoring, audits, IRB/IEC review, and regulatory agency inspections and provide direct access to source documents or certified copies for such review and inspection.

The sponsor or designee is responsible for the data management of this study including quality checking of the source data.

Study monitors will perform ongoing source data verification to confirm that data entered in the eCRF by authorized site personnel are attributable, legible, contemporaneous, original, accurate, and complete. Changes to source data must be traceable, not obscure the original entry, and be fully explained if necessary (e.g., via an audit trail). The safety and rights of participants must be protected, and the study conducted in accordance with the currently approved protocol and any other study agreements, ICH GCP, and all applicable regulatory requirements.

Quality tolerance limits (QTLs) will be predefined in the Study Management Plan to identify systematic issues that can impact participant safety and/or the reliability of study results. These predefined parameters will be monitored during the study. Important deviations from the QTLs and remedial actions taken will be summarized in the Clinical Study Report (CSR).

Study records and source documents pertaining to the conduct of this study, including signed ICFs, must be retained by the investigator for 15 years from issuance of the final CSR/equivalent summary unless local regulations or institutional policies require a longer retention period. No records may be destroyed during the retention period without the written approval of the sponsor. No records may be transferred to another location or party without written notification to the sponsor.

10.1.8. Source documents

Source documents provide evidence to establish the existence of the participant and substantiate the integrity of collected data. The investigator should maintain a record of the location(s) of their source documents.

Data transcribed into the eCRF from source documents must be consistent with those source documents; any discrepancies must be explained. The investigator may need to request previous medical records or transfer records, depending on the study. Also, current medical records must be available.

Definitions of what constitutes source data and documents can be found in the [Glossary of terms](#).

10.1.9. Study and site start and closure

First act of recruitment

The start of study is defined as FSFV.

Study/Site termination

GSK or its designee reserves the right to close the study site or terminate the study at any time for any reason at its sole discretion, provided there is sufficient notice given to account for all participants safe exit from study.

Regular closure of study sites will occur upon study completion. A study site is considered closed when all required data/documents and study supplies have been collected and a study site closure visit has been performed.

The investigator may initiate study site closure at any time, provided there is reasonable cause and enough notice in advance of the intended termination.

Reasons for the early closure of a study site by the sponsor or investigator may include but are not limited to:

- Failure of the investigator to comply with the protocol, the requirements of the IRB/IEC or local health authorities, the sponsor's procedures, or GCP guidelines
- Inadequate recruitment of participants by the investigator

- Discontinuation of further study intervention development
- Total number of participants included earlier than expected

If the study is prematurely terminated or suspended, the sponsor shall promptly inform the investigators, the IECs/IRBs, the regulatory authorities, and any contract research organization(s) used in the study of the reason for termination or suspension, as specified by the applicable regulatory requirements. The investigator shall promptly inform the participant and should assure appropriate participant therapy and/or follow-up.

10.1.10. Publication policy

GSK aims to submit the results of the study for publication in searchable, peer reviewed scientific literature within 18 months from the LSLV for interventional studies and follows the guidance from the International Committee of Medical Journal Editors (ICMJE).

10.2. Appendix 2: Clinical laboratory tests

10.2.1. Protocol required immunogenicity laboratory assessments

Anti-RV IgA antibody determination:

The anti-RV antibody concentrations are determined by a validated anti-RV IgA ELISA. Microtiter plates (96-well) are coated with an anti-RV monoclonal antibody. The wells are washed and incubated with (positive wells) or without (negative wells) RV. Following incubation, the plates are washed and serum, standard and control dilutions are incubated in both types of wells (positive and negative). Bound anti-RV IgA in the wells are detected by incubation with peroxidase conjugated anti-human IgA polyclonal antibodies. Color development proportional to the quantity of bound anti-RV IgA occurs in the presence of a chromogen, TetraMethylBenzidine, and measured spectrophotometrically. Specific optical densities are calculated for each sample/control/standard dilution by measuring the difference between positive and negative wells, the use of negative wells allowing to assess non-specific IgA binding. The concentrations of the samples expressed in units per milliliter are calculated relative to the four-parameter logistic function generated from the standard curve.

Anti-IPV type 1, type 2 and type 3 antibodies determination:

The polio microneutralization assay measures neutralizing antibody titers to poliovirus types 1, 2, and 3 using 96-well microtiter plates. The principle of the test is that the anti-poliovirus antibodies in a serum sample will bind to the virus and block infection of susceptible cells. Because poliovirus is cytopathic, virus that is not bound by antibody infects and lyses cells. The amount of neutralizing antibody is quantitated as a titer based on the last serum dilution to protect susceptible cell culture wells from poliovirus infection and cytopathic effect.

10.3. Appendix 3: AE: definitions and procedures for recording, evaluating, follow-up, and reporting**10.3.1. Definition of an AE**

- An AE is any untoward medical occurrence in a clinical study participant, temporally associated with the use of a study intervention, whether or not considered related to the study intervention.
- Note: an AE can therefore be any unfavorable and unintended sign (including an abnormal laboratory finding), symptom, or disease (new or exacerbated) temporally associated with the use of a study intervention.

10.3.1.1. Events Meeting the AE Definition

- Significant or unexpected worsening or exacerbation of the condition/indication under study.
- Exacerbation of a chronic or intermittent pre-existing condition including either an increase in frequency and/or intensity of the condition.
- New conditions detected or diagnosed after administration of the study intervention even though they may have been present before study start.
- Signs, symptoms, or the clinical sequelae of a suspected drug, disease or other interaction.
- Signs, symptoms, or the clinical sequelae of a suspected overdose of either the study intervention or a concurrent medication.
- Signs or symptoms temporally associated with administration of the study intervention.
- Signs, symptoms that require medical attention (e.g., hospital stays, physician visits and emergency room visits).
- Significant failure of an expected pharmacologic or biological action.
- Pre- or post- intervention events that occur as a result of protocol-mandated procedures (i.e., invasive procedures, modification of participant's previous therapeutic regimen).
- Clinically significant abnormal laboratory findings or other abnormal assessments that are present at baseline and significantly worsen following the start of the study will also be reported as AEs or SAEs.
- AEs to be recorded as solicited AEs are described in Section 10.3.3. All other AEs after administration of *Rotarix* will be recorded as unsolicited AEs.
- The signs, symptoms, and/or clinical sequelae resulting from lack of efficacy will be reported as AE or SAE if they fulfill the definition of an AE or SAE.

10.3.1.2. Events NOT Meeting the AE Definition

- Situations where an untoward medical occurrence did not occur (e.g., social and/or convenience admission to a hospital, admission for routine examination).
- Anticipated day-to-day fluctuations of pre-existing disease(s) or condition(s) present or detected at the start of the study that do not worsen.
- Pre-existing conditions or signs and/or symptoms present in a participant before the first dose of study intervention. These events will be recorded in the medical history section of the eCRF.
- Hospitalization for elective treatment of a pre-existing condition (known or diagnosed before signing the informed consent) that did not worsen from baseline.
- Any clinically significant abnormal laboratory findings or other abnormal safety assessments associated with the underlying disease, unless judged by the investigator to be more severe than expected for the participant's condition.

10.3.2. Definition of an SAE**An SAE is any untoward medical occurrence that:**

a. Results in death.

b. Is life-threatening.

Note: the term 'life-threatening' in the definition of 'serious' refers to an event in which the participant was at risk of death at the time of the event. It does not refer to an event, which hypothetically might have caused death, had it been more severe.

c. Requires hospitalization or prolongation of existing hospitalization.

Note: in general, hospitalization signifies that the participant has been admitted (usually involving at least an overnight stay) at the hospital or emergency ward for observation and/or treatment that would not have been appropriate in the physician's office or outpatient setting. Complications that occur during hospitalization are AEs. If a complication prolongs hospitalization or fulfills any other serious criteria, the event is serious. When in doubt as to whether "hospitalization" occurred or was necessary, the AE should be considered serious.

Hospitalization for elective treatment of a pre-existing condition that did not worsen from baseline is not considered an AE.

d. Results in disability/incapacity.

Note: the term disability means a substantial disruption of a person's ability to conduct normal life functions. This definition is not intended to include experiences of relatively minor medical significance such as uncomplicated headache, nausea, vomiting, diarrhea, influenza like illness, and accidental trauma (e.g., sprained ankle) which may interfere or prevent everyday life functions but do not constitute a substantial disruption.

e. Other situations.

Medical or scientific judgment must be exercised in deciding whether reporting is appropriate in other situations. Important medical events that may not be immediately life-threatening or result in death or hospitalization but may jeopardize the participant or require medical or surgical intervention to prevent one of the other outcomes listed in the above definition should be considered serious. Examples of such events are invasive or malignant cancers; intensive treatment in an emergency room or at home for allergic bronchospasm; blood dyscrasias; and convulsions that do not result in hospitalization.

10.3.3. Solicited events

Definition of solicited event

- Solicited events are predefined events-administration site events and systemic events for which the participant's parent(s) /LAR(s) is specifically questioned, and which are noted by the participant's parent(s) /LAR(s)] in their diary/eDiary.

Note: for this study solicited systemic events will be collected post Dose 1 and Dose 2 of study interventions administration.

The following events will be solicited:

Table 17 Solicited systemic events

Fever
Diarrhea
Vomiting
Irritability/Fussiness
Loss of appetite
Cough/runny nose

Note: participants' parent(s)/LAR(s) will be instructed to measure and record the body temperature in the evening. Should additional temperature measurements be performed at other times of day, participants' parent(s)/LAR(s) will be instructed to record the highest temperature in the diary card.

10.3.4. Unsolicited AE

Definition of unsolicited AE

- An unsolicited AE is an AE that is either not included in the list of solicited events or is included in the list of solicited events but has an onset outside the specified period of follow-up for solicited events. Unsolicited AEs must be communicated by participant's parent(s)/LAR(s) who has signed the informed consent. Unsolicited AEs include both serious and nonserious AEs.

- Potential unsolicited AEs may be medically attended (i.e., symptoms or illnesses requiring a hospitalization, emergency room visit, or visit to/by a healthcare provider). The participant's parent(s)/LAR(s) will be instructed to contact the site as soon as possible to report medically attended event(s), as well as any events that, though not medically attended, are of participant's parent(s) /LAR(s) concern. Detailed information about reported unsolicited AEs will be collected by qualified site personnel and documented in the participant's records.
- Unsolicited AEs that are not medically attended nor perceived as a concern by the participant's parent(s)/LAR(s) will be collected during an interview with the participant's parent(s)/LAR(s) and by review of available medical records at the next visit.
- Note: for this study unsolicited AEs will be collected post Dose 1 and post Dose 2 of *Rotarix* administration.

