
 To evaluate the reactogenicity of Rotarix PCV-free and IPV in terms of solicited systemic events. To assess the safety of Rotarix PCV-free in terms of unsolicited AEs and serious adverse events (SAEs) and safety of IPV in terms of SAEs. 	
 Solicited AEs 
 For each solicited systemic event, percentage of participants reporting the occurrence of the event within 14 days (Day 1- Day 14) after Dose 1 and Dose 2 of Rotarix and IPV Unsolicited AEs 
 Percentage of participants reporting the occurrence of unsolicited AEs within 31 days (Day 1- Day 31) after each dose of Rotarix, according to the MedDRA classification. SAEs: 
 Percentage of participants reporting SAEs from the first dose of the study intervention up to study end in the Co-administration and Staggered groups.

Ab: Antibody; GMC: Geometric mean Ab concentration; GMT: Geometric mean Ab titer; IgA: Immunoglobulin A; IPV: Inactivated poliovirus vaccine; MedDRA: Medical Dictionary for Regulatory Activities; mL: milliliter; PCV: *Porcine circovirus*; SAE: Serious Adverse Event; U: Unit

*Seroconversion rate for IPV neutralizing Ab is defined as percentage of participants with

- Titer $\geq 1:8$ at 1 month after 3 dose primary schedule of IPV in participants with titer $< 1:8$ pre-vaccination
- Titer ≥ 4 -fold increase in titer 1 month after 3 dose primary vaccination schedule in participants with titer $\geq 1:8$ pre-vaccination.

Note: the 4-fold increase will take into consideration the expected decline in maternal antibodies with estimated half-life of 28 days.

**Seroconversion rate for anti-RV IgA Ab is defined as the percentage of participants who were initially seronegative (i.e., with anti-RV IgA Ab concentration < 20 U/mL prior the first dose of *Rotarix*) and developed anti-RV IgA Ab concentration ≥ 20 U/mL at 1 month post Dose 2.

Refer to Section 8 for details on SAEs.

Refer to Section 9.3 and Section 9.4 for additional details on statistical analyses.

[figure not shown]
Details related to attributes of estimand covering intercurrent events, population and treatment definition are provided in the Section 9.

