8.2.1.4. Warnings and precautions to administration of study interventions

Warnings and precautions to administration of study intervention must be checked at each visit with planned administration of study intervention as specified in SoA (Section 1.3).

Refer to the approved product label/package insert.

8.3. Adverse Events (AEs), Serious Adverse Events (SAEs) and other safety reporting**8.3.1. Time period and frequency for collecting AE, SAE and other safety information**

An overview of the protocol required reporting periods for safety information and for AEs/SAEs leading to withdrawal is given in [Table 11](#) and [Table 12](#).

The investigator or designee will record and immediately report all SAEs in enrolled participants to the sponsor or designee via the Expedited AE Reporting Form. Reporting should, under no circumstances, occur later than 24 hours after the investigator becomes aware of an SAE, as indicated in Section 10.3.8. The investigator will submit any updated SAE data to the sponsor within 24 hours of it being available.

A post-study AE/SAE is defined as any event that occurs outside of the AE/SAE reporting periods defined in [Table 11](#). Investigators are not obligated to actively seek AEs or SAEs from former study participants. However, if the investigator learns of any SAE, including a death, at any time after a participant has been discharged from the study, and if the investigator considers the event to be reasonably related to the study intervention, the investigator will promptly notify the study contact for reporting SAEs mentioned in the [Table 13](#).

Table 11 Timeframes for collecting and reporting of safety information

Event	V1 ⁺ D1	V2 ⁺ M0.5	V3 ⁺ M1	V4 ⁺ M1.5	V5 ⁺ M2	V6 ⁺ M2.5	V7 ⁺ (Study Conclusion) M 3.5
Solicited events Co-ad group							
Solicited events Staggered group							
Unsolicited AEs Co-ad group*							
Unsolicited AEs Staggered group*							
AEs that led to withdrawal from the study							
SAEs							
SAEs related to study participation** or concurrent GSK medication/ vaccine							

AE: Adverse Event; Co-ad: Co-administration group; V: Visit; D: Day, M: Month; SAE: Serious Adverse Event

* Unsolicited AEs will be collected only post *Rotarix* administration.

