10.3.7.3. Medically attended visits

For each solicited (post administration of Dose 1 and Dose 2 of *Rotarix* and IPV) and unsolicited symptom (post *Rotarix* administration) the participant experiences, the participant's parent(s)/LAR(s) will be asked if the participant received medical attention defined as hospitalization, or an otherwise unscheduled visit to or from medical personnel for any reason, including emergency room visits. This information will be recorded in the eCRF.

Medical attention received for SAEs will have to be reported using the normal AE reporting process in the eCRF.

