
 To evaluate the reactogenicity of Rotarix PCV-free and IPV in terms of solicited systemic events. To assess the safety of Rotarix PCV-free in terms of unsolicited AEs and serious adverse events (SAEs) and safety of IPV in terms of SAEs. 	
 Solicited AEs 
 For each solicited systemic event, percentage of participants reporting the occurrence of the event within 14 days (Day 1- Day 14) after Dose 1 and Dose 2 of Rotarix and IPV Unsolicited AEs 
 Percentage of participants reporting the occurrence of unsolicited AEs within 31 days (Day 1- Day 31) after each dose of Rotarix, according to the MedDRA classification. SAEs: 
 Percentage of participants reporting SAEs from the first dose of the study intervention up to study end in the Co-administration and Staggered groups.

Ab: Antibody; GMC: Geometric mean Ab concentration; GMT: Geometric mean Ab titer; IgA: Immunoglobulin A; IPV: Inactivated poliovirus vaccine; MedDRA: Medical Dictionary for Regulatory Activities; mL: milliliter; PCV: *Porcine circovirus*; SAE: Serious Adverse Event; U: Unit

*Seroconversion rate for IPV neutralizing Ab is defined as percentage of participants with

[figure not shown]
- Titer $\geq 1:8$ at 1 month after 3 dose primary schedule of IPV in participants with titer $<1:8$ pre-vaccination
- Titer ≥ 4 -fold increase in titer 1 month after 3 dose primary vaccination schedule in participants with titer $\geq 1:8$ pre-vaccination.

Note: the 4-fold increase will take into consideration the expected decline in maternal antibodies with estimated half-life of 28 days.

**Seroconversion rate for anti-RV IgA Ab is defined as the percentage of participants who were initially seronegative (i.e., with anti-RV IgA Ab concentration <20 U/mL prior the first dose of *Rotarix*) and developed anti-RV IgA Ab concentration ≥ 20 U/mL at 1 month post Dose 2.

** complementary details on estimand including impact of intercurrent events on the analysis is available in Section 3 and Section 4.

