4.5. Safety Analyses

The analyses will be descriptive and conducted on the ES.

The following calculations will be performed for each group:

- The percentage of doses and participants reporting at least 1 AE (solicited or unsolicited) during the 14-day (Day 1 to Day 14) solicited follow-up period will be computed, along with exact 95% CI. The same calculations will be done for AEs (solicited or unsolicited) rated as grade 3 in intensity and for AEs leading to a medically attended visit.
- The percentage of doses over the study and the percentage of participants (by dose and over the study) reporting each individual solicited systemic event will be computed, over the 14-day (Day 1 to Day 14) solicited follow-up period, following study intervention administration, along with exact 95% CI. The same calculations will be done for each individual solicited systemic event rated as grade 3 (grade 3 or grade 4 for fever) in intensity and events leading to a medically attended visit. Temperature above specific thresholds will also be summarized with threshold defined by half degree increment.

Note: Intensity of fever will be assessed by considering the grading scales recommended by the Chinese authorities [NMPA, 2019].

- The verbatim reports of unsolicited AEs will be reviewed by a physician and will be coded according to MedDRA. Every verbatim term will be matched with the appropriate Preferred Term. The percentage of participants with unsolicited AEs occurring within 31-day (Day 1 to Day 31) follow-up period after any dose of *Rotarix* PCV-free with its exact 95% CI will be tabulated by Preferred Term. The same calculations will be done for each AE rated as grade 3 in intensity, for AEs leading to a medically attended visit and for AEs causally related to HRV as per the investigator assessment.
- The percentage of participants reporting the occurrence of SAEs (any, related, fatal, fatal related) from Dose 1 of the study intervention up to study end with its exact 95% CI will be tabulated by study group and by preferred term.
- The percentage of participants reporting the occurrence of SAEs (any, related, fatal, fatal related) within 31-day (Day 1 to Day 31) follow-up period after any dose with its exact 95% CI will be tabulated by study group and by preferred term.
- SAEs and dropouts due to AEs will be described in detail.

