6.2.4.3. Unsolicited adverse events

Unsolicited AE summaries will include unsolicited AEs and SAEs. Solicited events collected within the Day 1 -14 assessment period will be reported in the clinical event (CE) domain while unsolicited events will be reported in the AE domain. Following CBER's request to comply with the CDISC Vaccines Therapeutic Area Guide, solicited events that continue beyond the assessment period will also be reported in the AE domain. These solicited events will not be included in the summaries of unsolicited AEs but will be reported separately.

Missing severity, relationship with study vaccine, and outcome of unsolicited adverse events will not be replaced and will appear as 'UNKNOWN' in all statistical output.

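### Non-serious Table 17 symptoms starting on about Rotarix Days 16–29 count as unsolicited AEs in Co-administration but fall in the IPV solicited window in Staggered, so the by-group unsolicited AE percentages are not comparable

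*Protocol*

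**What the plan says.** Protocol 10.3.3 (Table 17) lists six solicited systemic events: fever, diarrhea, vomiting, irritability/fussiness, loss of appetite and cough/runny nose. It states that "for this study solicited systemic events will be collected post Dose 1 and Dose 2 of study interventions administration". The endpoint in Protocol Section 3, which applies to both vaccines, is the "percentage of participants reporting the occurrence of the event within 14 days (Day 1- Day 14) after Dose 1 and Dose 2". Protocol 10.3.7.3 confirms that IPV doses have their own solicited follow-up: "For each solicited (post administration of Dose 1 and Dose 2 of *Rotarix* and IPV) and unsolicited symptom".

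Under Protocol 10.3.4, a listed symptom becomes unsolicited only when it "is included in the list of solicited events but has an onset outside the specified period of follow-up for solicited events". Unsolicited events are tied to Rotarix alone. The footnote to Protocol Table 11 says "Unsolicited AEs will be collected only post *Rotarix* administration", and the endpoint in SAP 1.1 is "Percentage of participants reporting the occurrence of unsolicited AEs within 31 days (Day 1- Day 31) after each dose of" that vaccine.

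SAP 4.5 tabulates this by group, again for Rotarix doses only: "The percentage of participants with unsolicited AEs occurring within 31-day (Day 1 to Day 31) follow-up period after any dose of" that vaccine. Further tables cover Grade 3, medically attended and HRV-related events. On data structure, SAP 6.2.4.3 says "Solicited events collected within the Day 1 -14 assessment period will be reported in the clinical event (CE) domain", with unsolicited events going to the AE domain.

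Neither document has a rule for an IPV solicited window that falls inside a Rotarix Day 1–31 period.

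**The concern.** The classification of the same symptom depends on the dosing schedule. Take a fever that starts on Day 20 after Rotarix. In Co-administration the only solicited window closed on Day 14, so the fever is an unsolicited AE. In Staggered, IPV was given about Day 16, so the fever falls in the IPV solicited window, goes to the CE domain and is not tabulated as unsolicited. Counting onset day from the Rotarix dose would not change this, because the cause is the definition and not the day count.

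A trial meant to assess the safety of co-administration will have its by-group percentages read side by side. An excess in Co-administration that comes from classification could be taken for an effect of giving the vaccines together. Protocol 9.3.2 recognises the same kind of problem for anti-RV IgA and declines to compute group differences because the Rotarix schedules differ. No such caution is attached to unsolicited AEs.

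**Working it through.** The plan states no figure for this point, so there is none to reproduce.

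**Inputs**
- Solicited window: Days 1–14 after Doses 1 and 2 of each vaccine (Protocol Section 3).
- Unsolicited window: Days 1–31 after each Rotarix dose (Protocol Section 3, SAP 4.5).
- Co-administration: both vaccines together, 30 days apart at the optimum, 28–36 allowed (Protocol Table 3).
- Staggered: IPV Dose 1 at 15 days after Rotarix Dose 1 (14–18 allowed); Rotarix Doses 1 to 2 and IPV Doses 1 to 2 each 30 days apart (28–36 allowed) (Protocol Table 4).

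**Day count at optimal spacing** (Rotarix Dose 1 on day 0)
- The two Rotarix periods cover days 0–30 and 30–60, a union of 61 days in each group.
- Co-administration solicited days: 0–13 and 30–43, which is 28. Remaining: 61 − 28 = 33.
- Staggered solicited days: 0–13, 15–28, 30–43 and 45–58, which is 56. Remaining: 61 − 56 = 5.
- In Rotarix days, the IPV window in Staggered covers Days 16–29 after each dose. Day 15 and Day 30 after both doses, and Day 31 after Dose 2, remain unsolicited in both groups (2 + 3 = 5).

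**Allowed intervals**
- After Rotarix Dose 1, a gap to IPV of 14–18 days covers 13 or 14 of the 17 days from Day 15 to Day 31.
- After Rotarix Dose 2, the gap to IPV has no window of its own. From Table 4 it is (14 to 18) + (28 to 36) − (28 to 36), so 6 to 26 days, and it covers 5 to 14 of the 17 days.
- Over all combinations, the countable days are 31–34 in Co-administration and 3–16 in Staggered. The ranges do not overlap.
- Under the special-circumstances intervals, a Rotarix-to-IPV gap above 30 days after Dose 1 removes the overlap for that dose.

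**Illustrative size**

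The documents give no background rate, so it is assumed. Let x be the share of infants with a new listed symptom per 14 days, the same in both groups, with no vaccine effect. Let r be the fraction reported and d the countable days.

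λ = −ln(1 − x)/14, and P = 1 − exp(−r·λ·d).

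For x = 10%, λ = 0.10536/14 = 0.007526. With r = 1:
- Co-administration: 1 − exp(−0.007526 × 33) = 22.0%
- Staggered: 1 − exp(−0.007526 × 5) = 3.7%

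| x | r | Days (Co-ad vs Staggered) | Co-administration | Staggered |
|---|---|---|---|---|
| 5% | 1 | 33 vs 5 | 11.4% | 1.8% |
| 10% | 1 | 33 vs 5 | 22.0% | 3.7% |
| 20% | 1 | 33 vs 5 | 40.9% | 7.7% |
| 10% | 0.5 | 33 vs 5 | 11.7% | 1.9% |
| 10% | 0.25 | 33 vs 5 | 6.0% | 0.9% |
| 10% | 1 | 31 vs 16 (narrowest) | 20.8% | 11.3% |

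**Other planned outputs**

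The combined solicited-or-unsolicited table in SAP 4.5 is limited to the 14-day windows (28 days against 56), so it omits the later onsets at issue. SAP 6.2.4.3 deals with solicited events that continue past their window, not with new onsets.

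**The case against.** The strongest reply is that no planned comparison is affected. SAP 4.5 calls the safety analyses descriptive, Protocol 9.4.1 places them under within-group assessment, and the objective concerns the safety of Rotarix itself. Results are shown by Preferred Term, so an excess confined to fever, diarrhea or cough would be visible. This stands. It limits the problem to a misleading side-by-side reading, but it does not make the percentages comparable.

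A reader might infer several stronger things that the documents do not support:
- **That every listed symptom on Rotarix Days 15–31 is affected.** At optimal spacing only Days 16–29 are.
- **That such an event can never reach the unsolicited tables in Staggered.** SAP 6.2.4.3 includes SAEs in the unsolicited summaries, so a serious listed symptom may still appear. Protocol 10.3.6.1 asks for the diagnosis to be recorded in place of its symptoms, so a fever diagnosed as an infection can be unsolicited in both groups. Grade 3 and medically attended events are the likeliest to carry a diagnosis, so the imbalance there is probably smaller.
- **That the HRV-related row must be higher in Co-administration by definition.** That row also depends on the investigator's causality judgment (Protocol 10.3.7.2).
- **That the gap will be as large as the full-reporting figures.** Outside solicited windows, events come from parent contact or an interview at the next visit (Protocol 10.3.4), not from a diary. Unaffected event types also dilute the contrast in the overall row.

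Two objections to possible remedies also stand. Removing the six types from the main table would conflict with the definition in Protocol 10.3.4. A table pooling the CE and AE domains would set diary-prompted Staggered events, soon after a fresh IPV dose, against interview-reported Co-administration events.

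**Conclusion.** The concern holds as a comparability problem in a descriptive secondary safety endpoint. The protocol's own definitions and schedule give listed symptoms 33 countable days in Co-administration against 5 in Staggered at optimal spacing, and 31–34 against 3–16 over the allowed intervals. Nothing in either document resolves this. The direction is towards higher percentages in Co-administration when the true risk is equal.

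The day counts rest only on the documents. The percentages are illustrations. They assume a constant background rate, no vaccine effect, and the same reporting fraction in both groups on countable days. Only non-serious Table 17 symptoms not recorded as a diagnosis are clearly affected. The primary non-inferiority objective is untouched. The change should be made, but the trial's main conclusion does not depend on it.

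**What to change.** In SAP 4.5, keep the protocol-defined unsolicited AE tables. Then:

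1. Add a supplementary by-group version (any, Grade 3, medically attended, HRV-related) that excludes Table 17 event types in both groups. Use a mapping from Preferred Terms to Table 17 types that is fixed before database freeze and states how diagnoses are treated.
2. Footnote the main tables to say that the IPV solicited window in Staggered makes the groups non-comparable for these terms.
3. If Table 17 types with onset on Rotarix Days 15–31 are also tabulated from the CE and AE domains together, label that table as subject to unequal ascertainment (diary against interview) and to fresh IPV exposure in Staggered.
4. Record the addition in SAP 4.8, which at present reports no changes to the protocol-defined analyses.

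The supplementary table removes the classification effect for these event types and needs no new data. The cost is one or two extra outputs and the work of agreeing the term mapping.
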